Metopimazine was rapidly metabolized to metopimazine acid, with metopimazine acid C_{max} occurring at median times ranging from 2 to 3 hours after dosing across cohorts. The mean metopimazine acid elimination $t_{1/2}$ ranged from 2.7 to 3.5 hours. Relative to parent metopimazine, plasma metopimazine acid exposure was generally 3- to 4-fold higher for C_{max} and 6- to 11-fold higher for AUC. For metopimazine, a close to dose proportional increase was observed for C_{max} , AUC from time 0 to the last measurable concentration (AUC_{0-last}) and AUC_{0-inf} . Accumulation of metopimazine acid was observed after repeated doses (Q6H) with a mean accumulation ratio of 1.6 to 1.7 based on C_{max} and 1.7 to 1.9 based on AUC_{0-6} .

Safety

No serious adverse events (SAEs) were observed during the study, and no participants withdrew due to adverse events (AEs). All adverse events (AEs) were reported to be mild or moderate in severity. No symptoms suggestive of neuroleptic malignant syndrome (NMS) or extrapyramidal symptoms (EPS) were observed and there were no clinically relevant changes in electrocardiogram (ECG) time intervals. No notable trends were observed in changes in laboratory tests.

An increased risk of orthostatic hypotension (OH) was observed with metopimazine, likely due to inhibition of peripheral adrenergic alpha-1 receptors. Orthostatic changes in vital signs considered to be clinically significant were defined as a decrease in systolic or diastolic blood pressure (BP) of at least 20 mm Hg or 10 mm Hg, respectively, or heart rate increase of at least 30 beats/minute and/or heart rate above 120 beats/minute ([Freeman et al. 2011; NIH-NINDS Postural Tachycardia Syndrome Information Page 2019](#)).

In the 15 mg and 30 mg groups of the SAD portion of the study, 1 to 2 participants (out of 6 in each dose group) were reported to have “dizziness in standing position”. No vital sign measurements were obtained at the time of these events; however, the preferred term of OH was recorded. A protocol amendment was implemented after cohort 2 (30 mg) of the SAD portion of the study to require vital sign measurements lying, sitting, and standing at prescribed timepoints after dosing. In the 45 mg and 60 mg groups of the SAD, 4 participants (out of 6 in each dose group) experienced OH.

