Two participants in the MAD 15 mg Q6H group experienced OH (on Day 1 at Hour 1 after the first dose) and 1 participant in the MAD 30 mg Q6H group experienced OH (on Day 1 at Hour 1 after the first dose). No other episodes of OH occurred with subsequent dosing in these participants, and no other participants in these dose groups experienced OH. On the other hand, most participants in the MAD 45 mg Q6H group experienced OH, and more than half experienced episodes on multiple days during the dosing period. A similar trend was noted for orthostatic tachycardia.

Based on these results, the risk of OH appeared to be dose dependent, with the 45 mg and 60 mg doses associated with a higher risk for OH than the 15 mg and 30 mg doses. These data also suggest that with repeat dosing, participants adapt to the alpha-adrenergic inhibition, which is consistent with the literature on alpha-1 receptor antagonists approved for use in hypertension and benign prostatic hyperplasia ([Achari et al. 1998](#)).

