2.3. Study Rationale

The purpose of this study is to evaluate the safety and efficacy of NG101 when administered orally across a range of 3 doses to participants aged 18 years or older with diabetic or idiopathic gastroparesis. Results of this study will guide optimal dose selection for phase 3.

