2.5.1. Risk Assessment

Potential Risk of Clinical Significance	Summary of Data / Rationale for Risk	Mitigation Strategy
Study Drug		
Orthostatic hypotension (OH)	
OH has been observed in the phase 1 studies with metopimazine free base (Vogalene) and NG101. This is likely due to partial alpha-1 receptor inhibition.
	
Exclusion criterion: Participants with severe postural symptoms and/or absolute systolic BP < 90 mm Hg upon standing.
 
Monitoring: During the study, participants will be observed in the clinic on Day 1 for 3 hours after taking the first dose of NG101 (approximately 1 to 2 hours after the time of maximum concentration [T_{max}]). At the Week 1 and Week 2 visits, participants will be observed for 2 and 3 hours after dosing, respectively. Participants will have hourly orthostatic BP and AE assessments while in the clinic for these visits.
 
Participants who have systolic BP that decreases at least 20 mm Hg upon standing, and who have concomitant postural AEs during study visits will be further assessed in the clinic and/or after returning home. Postural AEs can include feelings of lightheadedness, general weakness, warmth, diaphoresis, nausea, palpitations or blurry vision (Whitledge et al. 2019).
 
If, in the investigator's judgement, a participant's postural symptoms constitute a safety risk of potential harm upon release from the clinic, that participant will remain in the clinic under observation (beyond the scheduled observation on Day 1 and Weeks 1 and 2) with continued orthostatic BP and AE assessments. If the participant has persistent moderately symptomatic OH through the 6-hour dosing interval, or the investigator has significant concern that BP decreases and postural symptoms will recur upon subsequent dosing, the participant should receive the next dose under observation in the clinic.
 
If, in the investigator's medical judgement, the participant continues to be at significant risk of harm with continued dosing upon release from clinic, that participant will be stopped and withdrawn from the study. Otherwise, once the participant is asymptomatic for OH on 2 successive measurements, the participant may be released from the clinic, and will be contacted by phone after returning home that day, and on subsequent days as necessary, to monitor for

Potential Risk of Clinical Significance	Summary of Data / Rationale for Risk	Mitigation Strategy

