Orthostatic hypotension (OH)	
Rationale: OH was observed in phase 1 studies, and likely occurs due to partial inhibition of α-1 receptors.
 
Criteria for diagnosis: OH is defined by a decrease in systolic BP of at least 20 mm Hg, and/or decrease in diastolic BP of at least 10 mm Hg, with associated severe postural symptoms.
 
Postural AEs can include feelings of lightheadedness, general weakness, warmth, diaphoresis, nausea, palpitations or blurry vision
 
(Whitledge et al. 2019). Severe postural symptoms include presyncope, syncope, and other severe AEs that are considered of substantial clinical relevance by the investigator. Presyncope is defined as “feeling like one was going to pass out but without actual loss of consciousness”
 
(Whitledge et al. 2019). Syncope is “the sudden loss of consciousness, associated with inability to maintain postural tone, with immediate and spontaneous recovery without requiring electrical or chemical cardioversion”
 
(da Silva 2014).

-------------------------------------	---

Abbreviations: AE = adverse event; AESI = adverse event of special interest; BP = blood pressure; CNS = central nervous system; D₂ = dopamine receptor; EPS = extrapyramidal symptoms; NMS = neuroleptic malignant syndrome; OH = orthostatic hypotension; ULN = upper limit of normal.

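### Orthostatic hypotension is worded differently as an adverse event of special interest and as a stopping criterion, the Week 1 orthostatic reading times conflict, and the protocol's analysis summary names no count of threshold crossings

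*Combined protocol and SAP*

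**What the plan says.** Incidence and severity of AESIs are part of the primary safety endpoint (Section 3), and Section 9.3.6 summarises AESIs by treatment group. Table 3 therefore sets what enters the OH AESI count.

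- **Section 8.5.7, Table 3.** OH is a systolic fall of at least 20 mm Hg and/or a "decrease in diastolic BP of at least 10 mm Hg, with associated severe postural symptoms". The table adds: "Severe postural symptoms include presyncope, syncope, and other severe AEs that are considered of substantial clinical relevance by the investigator".
- **Section 2.5.1, individual stopping criteria.** OH is defined by a systolic fall of at least 20 mm Hg. Severe postural symptoms are a further condition for stopping. There is no diastolic criterion.
- **Section 7.1, withdrawal criteria.** The pattern is the same: systolic only, with severe symptoms added. The reader is then sent to Table 3 for definitions.
- **Section 2.5.1, monitoring.** "At the Week 1 and Week 2 visits, participants will be observed for 2 and 3 hours after dosing, respectively". On what is measured during that observation, the section says: "Participants will have hourly orthostatic BP and AE assessments while in the clinic for these visits".
- **Section 8.4.2.** At Week 1, sitting and standing readings are taken before dosing and at 1 hour after dosing.
- **Sections 9.3.1 and 9.3.6.** Continuous variables get n, mean, SD, median, minimum and maximum; categorical variables get counts and percentages. TEAEs are summarised by arm, maximum severity and relationship. Vital signs get descriptive statistics.

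**The concern.** One term carries two meanings. In Table 3 severe symptoms are part of the diagnosis; in the stopping wording they are a condition added to it. Section 7.1 uses one meaning and refers to the other. A site or programmer following the text could classify the same event in two ways.

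This matters because OH is the main dose-dependent risk seen in phase 1 and the protocol says of this trial: "Results of this study will guide optimal dose selection for phase 3". If the AESI count mostly restates who met a withdrawal criterion, it adds little to a comparison of tolerability between arms. Summary statistics of blood pressure (BP) show the average and the extreme change, but not how many participants in each arm had a fall of the size that Table 3 names. The Week 1 mismatch affects data collection, so an analysis plan cannot repair it afterwards.

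**Working it through.** **Step 1. Classify the possible events under each wording.** Table 3 is read in its natural sense, with the symptom condition applying to both BP criteria.

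| Event on standing | AESI (Table 3) | OH as defined in 2.5.1 and 7.1 | OH stopping wording met |
|---|---|---|---|
| Systolic fall ≥ 20, severe symptoms | Yes | Yes | Yes |
| Diastolic fall ≥ 10 only, severe symptoms | Yes | No | No |
| Systolic fall ≥ 20, non-severe symptoms | No | Yes | No |
| Systolic fall ≥ 20, no symptoms | No | Yes | No |
| Diastolic fall ≥ 10 only, no severe symptoms | No | No | No |

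Row 1 shows the overlap of AESI and withdrawal for systolic falls. Row 2 shows an AESI that the OH stopping wording does not reach, although the general adverse-event criterion in Section 7.1 could still apply. In rows 3 and 4 the event is OH in one section and not in the other.

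**Step 2. Test the other reading of Table 3.** If the symptom condition applied only to the diastolic criterion, rows 3 and 4 would become AESIs. The mismatch would shrink, but the count would mean something quite different. The wording needs settling under either reading.

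**Step 3. Find where the non-AESI events go.** Postural symptoms are reported as adverse events, and a vital-sign change judged clinically significant is itself an adverse event (Section 10.5.1). Both then appear as TEAEs by arm and maximum severity (Section 9.3.6). Two things remain: these events are absent from the AESI count, and falls with no reported event that are judged not clinically significant are in no count that the protocol names.

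**Step 4. Look for a threshold count.** Section 9.3.1 gives general methods and names no orthostatic category. Section 9.3.6 names none for vital signs. Section 9.3.5 lists an association of PK with safety assessments and names no orthostatic measure. Section 9.3 describes itself as a summary and leaves detail to the SAP.

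**Step 5. Compare the orthostatic schedules.** Both sections give 3 hours at Day 1 and Week 2. At Week 1, Section 2.5.1 implies post-dose readings at 1 and 2 hours and Section 8.4.2 gives 1 hour only, a difference of one reading per participant. The 20 mg arm takes 5 mg for 4 days and 10 mg for 3 days; 4 + 3 = 7, so 20 mg starts on Day 8 (Section 1.2), around the Week 1 visit.

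**Step 6. Try to size the loss.** Phase 1 multiple dosing (Section 2.2.1.1) recorded OH in 2 participants at 15 mg and 1 at 30 mg every 6 hours, in cohorts of 8. That is 2/8 = 25% and 1/8 = 12.5%; if 6 per cohort were on active drug (assumed from the single-dose part), 2/6 = 33% and 1/6 = 17%. The text does not say which of these 3 had presyncope. All adverse events were mild or moderate, but intensity is graded separately (Section 10.5.3) and Table 3 lists presyncope without an intensity condition. Table 3 could have counted anywhere from 0 to 3 of them, so these data give no size.

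**The case against.** The strongest reply is that little is lost. Limiting an AESI to clinically important events is a legitimate choice. Non-severe OH is still coded and tabulated by arm. The Data Safety Monitoring Board trigger uses discontinuations for OH-related events, not the AESI count (Section 9.5). Follow-up to resolution covers drug-related events as well as AESIs (Section 8.5.3). Minimum and maximum will show the largest falls. All of this stands, and it narrows the point.

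Some stronger readings are tempting, and the documents do not support them:

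- **That no threshold analysis is planned.** Section 9.3 defers detail to a SAP whose text was not available. Absence from a short summary section is weak evidence.
- **That phase 1 shows Table 3 to be wrong.** Clinically significant orthostatic changes there "were defined as a decrease in systolic or diastolic blood pressure (BP) of at least 20 mm Hg or 10 mm Hg, respectively", with heart-rate alternatives and no symptom condition. That is another study's threshold for vital-sign changes, not a case definition for this trial.
- **That the monitoring text is a rival definition.** "If the participant has persistent moderately symptomatic OH through the 6-hour dosing interval" is guidance on observation. Its use of the term should be aligned, but it defines nothing.
- **That a threshold table would show adaptation.** Section 4.2 gives assessing adaptation as a reason for the 20 mg titration, but no endpoint names it. In that arm the dose rises from 5 to 20 mg between Day 1 and Week 2, so adaptation and escalation cannot be separated.

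The reply does not touch the contradictions among Sections 2.5.1, 7.1, 8.4.2 and 8.5.7, which are in the protocol itself.

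**Conclusion.** The point holds in a limited form. The OH wording in Table 3 and in the two stopping passages is inconsistent on both the symptom condition and the diastolic criterion, and the Week 1 reading times conflict. These are plain protocol defects. The missing threshold count is conditional: the protocol's summary names none, and the SAP may.

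The size of the loss is unknown. It depends on how many participants have a 20/10 mm Hg fall without severe symptoms and how many of those falls lead to a reported event, and the documents give neither. The conclusion assumes the natural reading of Table 3, with the symptom condition applying to both BP criteria.

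**What to change.** 1. **Reconcile the OH wording** in the Section 2.5.1 stopping criteria, Section 7.1 and Table 3, and align the use of the term in the Section 2.5.1 monitoring text. Settle whether the diastolic criterion belongs and which BP criteria the symptom condition applies to. Keep the safety case definition separate from the stopping rule. Both are for the sponsor to set; no clinical rule is proposed here.
2. **Reconcile the Week 1 reading times** in Sections 2.5.1 and 8.4.2.
3. **Unless the SAP already has it, add one descriptive table** by arm, visit and time after dose: number and percent of participants whose sitting-to-standing change meets Table 3's own 20/10 mm Hg thresholds, regardless of symptoms. Show pre-dose status, because exclusion criterion 34 does not bar a participant who already has such a fall, and show the dose in use at each visit. State that in the 20 mg arm the table cannot separate adaptation from escalation. No between-arm test is needed.

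The cost is wording changes and one more table from readings already scheduled, with no new visits. The downside is a higher reported OH count. Comparison with phase 1 would stay limited, because phase 1 also measured lying BP and recorded some OH from dizziness without vital signs.

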8.6. Treatment of Overdose

For this study, participants are expected to take no more than 4 capsules in 1 day.

In the event of an overdose, participants should notify the investigator and the investigator should:

1. Contact the Medical Monitor immediately.
2. Continue to monitor the participant for any AE / SAE and laboratory abnormalities
3. Document the quantity of the excess dose.
4. Consider skipping the next dose of NG101. NG101 can be reinitiated, with the timing depending on the amount of overdose and considering the half-life of metopimazine (approximately 2 hours). Reinitiation should be discussed with the medical monitor.

Participants should be treated according to the symptoms they are experiencing. If a participant has symptoms suggestive of orthostasis, then the participant should sit down or lie down, depending on the severity of symptoms. Participants will be trained to recognize the signs and symptoms of OH.

Decisions regarding dose interruptions or modifications will be made by the investigator in consultation with the Medical Monitor based on the clinical evaluation of the participant.

8.7. Pharmacokinetics

Pharmacokinetic data collected in this study will be analyzed according to a separate PK Analysis Plan and reported separately from the primary study results.

As noted in [Section 8](#), when several procedures are scheduled at the same theoretical time and/or visit, study assessments should be performed in the following order: PRO assessments; 12-lead ECG; vital signs; blood samples.

8.7.1. Pharmacokinetic Assessment Methods and Timing

All participants will participate in PK assessment. A subset of participants who consent will participate in intensive PK sampling. The timing of blood sample collections is provided in [Table 4](#) below.

At the Day 1 and Week 2 visits, participants should arrive at the clinic after fasting (see [Section 5.3.1](#) for further details). Participants may have water during the fasting period, but no food should be consumed. Study drug should be taken 30 minutes before eating, at which point 240 mL of water should be provided with the dose. No additional water is permitted until 30 minutes after dosing, after which time, water is allowed ad libitum and a meal will be consumed.

Table 4: Pharmacokinetic Sampling Times

Study Day	Sparse PK		Intensive PK Subset
	PK Sample Timepoint (Hours after dose) (± Time window)	PK Sample Timepoint (Hours after dose) (± Time window)	PK Sample Timepoint (Hours after dose) (± Time window)
Day 1	Predose ^a		Predose ^a
	--		0.5 hours (± 5 minutes)
	1 hour (± 5 minutes)		1 hour (± 5 minutes)
	--		1.5 hours (± 5 minutes)
	2 hours (± 10 minutes)		2 hours (± 10 minutes)
	3 hours (± 10 minutes)		3 hours (± 10 minutes)
	--		4 hours (± 10 minutes)
	--		5 hours (± 10 minutes)
	--		6 hours (± 10 minutes)
	--	Administer second dose	
	--		1 hour (± 5 minutes)
	--		2 hours (± 10 minutes)
Week 2	Predose ^a		Predose ^a
	--		0.5 hour (± 5 minutes)
	1 hour (± 5 minutes)		1 hour (± 5 minutes)
	--		1.5 hours (± 5 minutes)
	2 hours (± 10 minutes)		2 hours (± 10 minutes)
	3 hours (± 10 minutes)		3 hours (± 10 minutes)
	--		4 hours (± 10 minutes)
	--		5 hours (± 10 minutes)
	--		6 hours (± 10 minutes)

Abbreviations: PK = pharmacokinetic

^a Within 15 to 20 minutes before dosing.

Note: For the Week 2 assessment in the Sparse PK group, participants should arrive at the clinic in the morning after fasting for at least 4 hours, and either prior to taking any study drug or within 4 to 6 hours after the first dose of study drug of the day.

Note: For the Week 2 assessment in the Intensive PK group, participants should arrive at the clinic in the morning after fasting for at least 8 hours and prior to the first dose of study drug of the day.

